3 STUDY ENDPOINTS

3.1 Primary Endpoint

Efficacy will be measured by the difference between treatment groups in the mean 6-point severity rating at Day 15. The severity ratings are:

1. Death
2. Hospitalized, on invasive mechanical ventilation or ECMO
3. Hospitalized, on non-invasive ventilation or high flow oxygen devices
4. Hospitalized, requiring supplemental oxygen
5. Hospitalized, not requiring supplemental oxygen
6. Not hospitalized

Six point severity ratings are from the 6-point ordinal rating scale eCRFs. Deaths through Day 15 from AE/SAE and subject disposition CRFs are also taken into account.

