							
within 48 hours of signing Informed Consent may be used as the Screening assessment. While subjects are in the hospital, vital signs will be collected once daily in the AM or PM but around the same time every day within 3 hours and entered on the eCRF.
 
After hospital discharge, vital signs should be collected at in-person visits on Days 22, 29, and 60 (if this is an in-person visit).

SpO2 and FiO2	X	X	X	X	X	X	
SpO2 and FiO2 collected as part of SOC within 48 hours of signing Informed Consent may be used as the Screening assessments. While the subject is in the hospital, this is collected in the eCRF once daily and should correlate (AM or PM) with the time the vital signs and the NEWS2 are collected.
 
After hospital discharge, SpO2 and FiO2 should be collected at any in-person visits on Days 22, 29, and 60 (if this is an in-person visit).

Procedure	Screening Visit Day -2 to Day 1	Baseline Visit (Randomization) Day 1	Days 2 through 14 (+/- 1 day)¹	End of Treatment (EOT) Visit or Day 15 (+/- 1 day)²	Post-Treatment Phase Days 16 (+/- 1 day) through Day 29³ (+/- 2 days)	Day 60 (+/- 15 days)	Comments
Arterial Blood Gas (ABG)							Arterial Blood Gas (ABG) is not a required assessment for the protocol. However, if it is collected as per SOC within 48 hours from signing Informed Consent through Day 29, this data should be entered in the eCRF in Unscheduled Visit ABG pages.
6-point ordinal scale	X	X	X	X	X	X	While in the hospital, this is collected once daily. This may be collected in the AM or PM at the discretion of the Investigator or staff but should be collect around the same time (within 3 hours) every day. If subjects are discharged from the hospital and unable to return for in-person visits, this scale should be assessed by phone on Days 15, 22, and 29. After hospital discharge, this assessment should be collected at in-person visits on Days 22, 29, and 60 (if an in-person visit).

Procedure	Screening Visit Day -2 to Day 1	Baseline Visit (Randomization) Day 1	Days 2 through 14 (+/- 1 day)¹	End of Treatment (EOT) Visit or Day 15 (+/- 1 day)²	Post-Treatment Phase Days 16 (+/- 1 day) through Day 29³ (+/- 2 days)	Day 60 (+/- 15 days)	Comments

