Telephone Visits				X	X	X	If subjects are released from the hospital prior to Day 15, and an EOT visit was conducted, a follow-up phone call should be made on Days 15, 22, and 29 to assess 6-point ordinal scale, AEs/SAEs, and concomitant medications and procedures. If the subject remains in the hospital on Days 15, 22, or 29, telephone visits are not required, but in-person visits should be conducted.

Procedure	Screening Visit Day -2 to Day 1	Baseline Visit (Randomization) Day 1	Days 2 through 14 (+/- 1 day)¹	End of Treatment (EOT) Visit or Day 15 (+/- 1 day)²	Post-Treatment Phase Days 16 (+/- 1 day) through Day 29³ (+/- 2 days)	Day 60 (+/- 15 days)	Comments
Safety Follow-up Visit (Day 60)						X	
If subjects have not had an in-person visit from the time of hospital discharge prior to Day 60, the Day 60 visit should be an in-person visit, and the same assessments that would have been collected on Day 29 should be performed.
 
If subjects have been able to have an in-patient or an in-person visit on Day 29, then the Day 60 visit will be done by telephone to collect 6-point ordinal scale, status of any AEs/SAEs ongoing at time of discharge, any new SAEs, and to confirm subject mortality.

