4.3.3.1 While Subjects are In the Hospital

During the Treatment Phase, while subjects are inpatient, SpO₂, FiO₂ and ongoing vitals will be collected **each day**. Although these procedures may be collected throughout the day as part of standard of care, for the purpose of data collection for this study, vitals, SpO₂, and FiO₂ will be collected in the eCRF **one time daily**. This data may be collected in the morning (AM) or evening (PM) but should be around the same time every day (within 3 hours) and entered on the eCRF. Arterial Blood Gas (ABG) is not a required assessment per protocol. However, if ABG

is collected as per SOC at any time within 48 hours prior to signing Informed Consent through Day 29, this data should be entered in the eCRF whenever it is collected on Unscheduled Visit ABG pages.

NEWS2 is a collection of ongoing vitals related to: respiration (breaths/min), SpO2 oxygen saturation (%), blood pressure (BP), pulse, consciousness, and temperature to provide a total NEWS2 score. While subjects are inpatient, NEWS2 should be assessed daily. The timing of the NEWS2 for the purpose of the data collection for the study should also correlate with the timing of the collection of the SpO2 and FiO2, and entered in the eCRF.

Subjects will have SAE/AEs monitored as well as concomitant medications and procedures daily.

Clinical safety labs, urinalysis, LFTs, ECGs, and chest x-rays will be collected as specified in [Table 1](#).

If the subject is admitted to the ICU, then SOFA2 will be collected upon admission to the ICU, and will be collected again if subject is still in the ICU at Day 29.

If during the treatment period, subjects are transferred to another care facility, they should continue on study drug with the expectation that the Investigator and Staff will coordinate with the treating facility to obtain, at minimum, safety and primary endpoint data and allow the subject to complete the trial as per protocol.

For the purpose of the 6-point ordinal primary endpoint scale, item number 6 (Not Hospitalized) means discharged from acute care. Transferring a subject to another acute care facility due to COVID-19 challenges does not qualify as a 6 on the ordinal scale. Any operational questions about logistics of a transferred subject should be addressed with the Biohaven Medical Monitor or designee.

If local administration site irritation develops, the PI should call the medical monitor to discuss the dosing plan.

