4.3.3.2 *If Subjects are Discharged Prior to Day 15*

If a subject is planned to be discharged from the hospital prior to completing treatment, they will be discontinued from study drug. The Investigator should discuss the discharge plan with the Medical Monitor.

Note: Due to the potential for rebound from withdrawal of an immunomodulating agent, if a subject is withdrawn from drug, they need to be monitored in the hospital for at least 24 hours before release. All End of Treatment (EOT) assessments (see Section 4.3.5) should be collected after the patient's last dose of study drug and prior to discharge. Although subjects will be discontinued from the study drug, they will remain in the study. If possible, subjects should continue with in-person visits as per [Table 1](#). If this is not possible due to COVID-19 restrictions, a phone call should be made to the subject on Days 15, 22, and 29 to collect these assessments: 6-point ordinal scale, AEs/SAEs, and concomitant medications and procedures. If

the subject is unable to return for in-person visits on Days 22 and 29 due to quarantine, subjects will need to return for at least 1 in-person visit on or before Day 60 to have the Day 29 in-person assessments completed.

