6.4 Efficacy Assessments

6.4.1 *6-point ordinal scale*

A 6-point ordinal scale will be collected for the Primary and secondary endpoints. The scale consists of the following anchor points:

1. Death
2. Hospitalized, on invasive mechanical ventilation or ECMO
3. Hospitalized, on non-invasive ventilation or high flow oxygen devices
4. Hospitalized, requiring supplemental oxygen
5. Hospitalized, not requiring supplemental oxygen
6. Not hospitalized

The 6-point ordinal scale will be collected each day the subject is in the hospital and at all in-person or telephone visits.

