9.3.2 Primary Endpoint

The primary endpoint will be analyzed using a Mixed Model for Repeated Measures (MMRM) with treatment group, visit, visit-by-treatment group interaction, and randomization stratum age group as fixed effects, baseline SpO₂/FiO₂ ratio as a covariate, and subject as a random effect. Visit will be a categorical variable based on analysis visit windows for Days 5, 10, 15, 22, and

29. The primary endpoint will be tested by comparing zavegeptant to placebo at Day 15 at an alpha level of 0.05. Descriptive statistics will be provided for each treatment group that show the number and percentage of subjects in each category. Analyses are based on the efficacy analysis set.

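### Read literally, the random subject effect in Section 9.3.2 gives all visits one variance and makes the Day 15 standard error too small, by an amount the protocol does not fix

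*Protocol*

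**What the plan says.** **Model.** Protocol Section 9.3.2 names an MMRM with treatment, visit, their interaction and age stratum as fixed effects. It closes the list with baseline SpO2/FiO2 "as a covariate, and subject as a random effect". The visits follow: "Visit will be a categorical variable based on analysis visit windows for Days 5, 10, 15, 22, and" 29. No other within-subject term or covariance structure is given. The test is the Day 15 contrast at 0.05, and under Section 9.3.3 it is the gate to the key secondary endpoints.

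**When ratings exist.** Section 6.4.1: "The 6-point ordinal scale will be collected each day the subject is in the hospital and at all in-person or telephone visits". For subjects discharged early, Section 4.3.3.2 says "a phone call should be made to the subject on Days 15, 22, and 29 to collect these assessments: 6-point ordinal scale". The ordinal-scale row of Table 1 likewise says "this scale should be assessed by phone on Days 15, 22, and 29", and the Telephone Visits row agrees. In-person ratings after discharge are set for Days 22, 29 and 60. Nothing is scheduled between discharge and Day 15.

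**What is filled in.** Section 3.1 takes ratings from the ordinal-scale form and adds: "Deaths through Day 15 from AE/SAE and subject disposition CRFs are also taken into account". It has no matching rule for discharge, although Section 4.3.3.1 says "item number 6 (Not Hospitalized) means discharged from acute care".

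**Missing data.** Section 9.3.5 expects little or none for the primary endpoint, relies on MAR, and promises sensitivity analyses under other assumptions.

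**The concern.** A random intercept implies the same variance at every visit and the same correlation between any two visits. Here the variances plainly differ. Section 9.1 expects subjects to enter mostly in category 4, so the spread is small early and grows as some recover and others worsen. The collection schedule widens the gap. A subject sent home on Day 7 is known to be a 6 on Day 10 but is blank in the model, and removing the 6s narrows the observed spread at Days 5 and 10 further.

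The model's single variance is therefore pulled below the Day 15 variance, and the Day 15 standard error is computed from it. At stake is the error rate of the one primary test, and through it the gate in Section 9.3.3. The size of the Day 15 estimate is not at stake.

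**Working it through.** **1. The plan's own figure.** Section 9.1 uses a t-test with 80 and 40 subjects, a 1-unit difference, SD 1.5 and alpha 0.05 (taken here as two-sided).
- SE = 1.5 × √(1/80 + 1/40) = 1.5 × 0.1936 = 0.290.
- Power from the noncentral t is 92.7%, against a stated rough 90%. The protocol hedges the figure, so this is not treated as an error.
- This SE uses the Day 15 variance alone. It is the benchmark below.

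**2. Why the estimate is safe but the SE is not.** With a visit-by-treatment interaction, no covariates, and Day 15 rated for everyone, the random-intercept estimate at Day 15 equals the raw Day 15 difference. Its SE is √[(σ²_subject + σ²_error)(1/80 + 1/40)], where the sum in the first bracket is one variance fitted to all five visits. The ratio to the correct SE is √(σ²_subject + σ²_error) / SD at Day 15.

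**3. How far below 1 the ratio falls.** The protocol gives no discharge rates, no SDs at other visits, no within-subject correlation and no window limits, so all courses are assumed.

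*Broad set.* Random daily courses on the six-point scale, 5 to 35% starting in category 3 and the rest in 4, Day 15 SD 1.45 to 1.55, no covariates:

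| Days 5 and 10 | Ratio, range | Median |
|---|---|---|
| 6s missing, 150 courses | 0.864–0.961 | 0.912 |
| 6s missing, another 100 | 0.874–0.976 | 0.912 |
| Nearest in-hospital rating, assumed ±2-day windows | 0.874–0.968 | 0.908 |
| 6s filled in | 0.93–0.99 | 0.963 |

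No course with the 6s missing reached 1. The shortfall is thus about 2 to 14%. Later visits help to set it. The lowest ratio (0.864) came from observed SDs of 0.85, 0.99, 1.48, 1.43 and 1.37 on Days 5 to 29. The highest of the 150 (0.961) came from 0.72, 0.84, 1.53, 1.71 and 1.85, where greater spread at Days 22 and 29 offsets the early visits.

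*Three fuller courses* (fast / middle / slow recovery; 65 / 55 / 43% home at Day 15), with subject frailty, readmission and all Section 9.3.2 covariates, Day 15 SD 1.5, 16,000 null trials each:

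| Model | SE shortfall, % | Type I error, % |
|---|---|---|
| Random intercept, 6s missing | 5.3 / 6.2 / 4.0 | 6.4 / 6.4 / 6.0 |
| Random intercept, 6s filled | 2.2 / 3.4 / 1.8 | 5.6 / 5.6 / 5.4 |
| Unstructured, 6s missing | 0.4 / 1.3 / -0.3 | 5.1 / 5.3 / 4.9 |
| Unstructured, 6s filled | 0.4 / 1.3 / -0.2 | 5.2 / 5.3 / 5.0 |
| Day 15 data only | 0.4 / 1.4 / -0.1 | 5.1 / 5.3 / 5.1 |

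The Monte Carlo error of the type I rates is about 0.2 points. The mean Day 15 estimate agreed to 0.001 in all versions. Many unstructured fits with the 6s missing had not fully converged in this run. A rerun with a line search (3,000 null trials) gave type I error of 4.6 / 5.1 / 4.8% with the 6s missing and 4.6 / 5.2 / 4.8% filled.

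**4. Translation to type I error.** For ratio k, the actual two-sided level is 2[1 − Φ(1.96k)]. k = 0.98 gives 5.5%, 0.96 gives 6.0%, 0.91 gives 7.4% and 0.86 gives 9.2%.

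**5. Why an unstructured covariance cures it.** Days 15, 22 and 29 are complete in this scenario. With an unstructured covariance the likelihood splits into a part for those visits and a part for Days 5 and 10 given them, with separate parameters. The Day 15 variance then comes essentially from Day 15 data, whatever happens earlier.

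**The case against.** The strongest reply is that MMRM is often fitted with an unstructured covariance, that Section 9 refers to the SAP for full statistical detail, and that covariance structure, windows and derivations commonly belong there. This largely stands. The mere absence of a named structure is no fault, and under an unstructured SAP there is no SE problem. What remains is that Section 9.3.2 does state a subject term, and its literal meaning is a different model with a different standard error.

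Three stronger readings are tempting and not supported.

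- **That the MAR statement fails and the primary result is biased.** Blanks at Days 5 and 10 do arise because the value is 6. But the primary endpoint is Day 15, where a call is required, and the estimate there is unaffected if the calls are made.
- **That the protocol's SD of 1.5 implies one definite shortfall.** It does not. At that SD, courses differing only in assumed transitions span 2 to 14%, and Section 9.1 itself calls the SD speculation.
- **That the missing 6s must be filled to protect the primary test.** Filling them under a random intercept still leaves a shortfall of about 1 to 7%. Under an unstructured covariance it changes nothing that matters at Day 15.

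**Conclusion.** The concern holds conditionally and is modest in size. If the subject term in Section 9.3.2 is implemented as a random intercept, the Day 15 SE is about 2 to 14% too small and the primary test runs at roughly 5.5 to 9% instead of 5%. This rests on assumed courses with a Day 15 SD near 1.5, on the Day 15 calls being made, and on a two-sided test. The direction was the same in every course tried. The size cannot be narrowed from the document.

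The Day 5 and Day 10 contrasts are also affected. In the three fuller courses, with a drug effect added, true Day 10 differences of 0.43 / 0.45 / 0.44 were estimated as 0.19 / 0.22 / 0.25. No test is attached to them, so they add little weight.

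**What to change.** **Needed.** In Section 9.3.2, replace the random subject effect with an unstructured within-subject covariance across the five visits. Name in advance the structure to use if the fit does not converge, for example one with a separate variance per visit. If the SAP already says this, align Section 9.3.2 with it.

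**Optional, for the descriptive Day 5 and Day 10 contrasts only.** Score 6 at those visits where discharge from acute care before the visit is documented, and not after transfer to another acute care facility, readmission or death. Carry the death score to all later model visits. Where discharge is not documented, leave the rating missing. Sections 4.3.3.2, 6.6 and 7.2 suggest a discharge record should exist, although the visible text names no form field for the date.

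**Cost.** The needed change is wording only, and no new visits or measurements are required. The reported Day 15 SE rises, by about 5% in the three fuller courses and by up to 1/0.86 = 1.16 times at the extreme of the broad set. In the three courses, with true Day 15 differences of 0.44 / 0.48 / 0.51, power falls from 50 / 56 / 57% to 46 / 51 / 52%, partly because false precision is removed. Nothing is lost against Section 9.1, which already uses the Day 15 SD alone. A 5×5 unstructured fit with 120 subjects may fail to converge, hence the fallback.

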9.3.3 Secondary Endpoints

If the primary endpoint is significant at alpha :S 0.05, then the key secondary endpoints will be tested at an alpha level of 0.05 using the Holmes procedure.

CCI

Analyses are based on the efficacy analysis set.

9.3.4 Adjustment for Multiplicity

Multiplicity is addressed in this study using a gatekeeping procedure (see Section 9.3.3).

9.3.5 Missing Data

Since this study is expected to be conducted in a hospital setting, we expect little or no missing data for the primary endpoint. Every effort will be made to contact subjects that are released from the hospital before Day 15 by telephone and determine their status for the primary endpoint. The statistical model for the primary endpoint will include all subjects, and is valid under the assumption of Missing At Random (MAR). Sensitivity analyses will assess the model under other assumptions regarding missingness.

9.3.6 Analysis of Safety

The investigators determine the intensity of AEs and the relationship of AEs to study therapy. The investigators' terms are coded and grouped by system organ class using the latest version of the Medical Dictionary for Regulatory Activities (MedDRA) available. AEs are presented by system organ class and preferred term in descending order of overall frequency of events. If a subject had an AE with different intensities over time, then only the greatest intensity is reported.

Deaths, all AEs, and SAEs are listed for the enrolled analysis set.

The frequencies of the following safety events on study are summarized by treatment group and overall for the safety analysis set: SAEs; AEs by intensity and overall; treatment-emergent AEs by intensity and overall; AEs leading to study drug discontinuation; and treatment-emergent AEs by relationship to study drug.

Clinically significant laboratory test abnormalities on study will be identified as Grade 3 to 4 laboratory test results graded according to numeric laboratory test criteria in CTCAE Version 5.0 (2017), if available. Otherwise, if CTCAE grades are not available, then results will be graded

according to numeric laboratory test criteria in Division of AIDS (DAIDS) Table for Grading the Severity of Adult and Pediatric Adverse Events Corrected Version 2.1 (2017). If a subject has a laboratory test abnormality with different toxicity grades over time, then only the highest toxicity grade will be reported.

Further safety analyses will be described in the SAP.

9.3.7 *Futility Analysis*

A formal futility analysis will be performed by the DMC statistician after approximately 50% of subjects complete the 14-day treatment period.

The DMC will test for futility stopping only. This test will not be counted against the alpha spend for the study. In particular, zavegeptant will be tested for inferiority to placebo, on the primary endpoint (the six point, ordinal, severity scale). This will be done using a Wilcoxon rank sum test at a one-sided alpha level of 0.05.

9.4 Schedule of Analyses

A futility analysis will be conducted by the DMC statistician after approximately half of the subjects have reached Day 15.

The first planned analysis for this study may be executed after the last subject has reached Day 29 of the study, and the database has been locked. The last planned analysis will occur after the last subject has completed the Day 60 safety follow up.

Additional unplanned analyses may be executed as needed to protect subject safety and as requested by regulatory agencies.

10 ETHICS AND RESPONSIBILITIES

10.1 Good Clinical Practice

This study will be conducted in compliance with the protocol, Good Clinical Practice (GCP), Good Laboratory Practice (GLP), International Conference on Harmonization (ICH) guidelines, and all applicable regulations, including the Federal Food, Drug and Cosmetic Act, U.S. applicable Code of Federal Regulations (title 21), any Independent Ethics Committee (IEC) requirements relative to clinical studies. The study will also be conducted in compliance with the recommendations laid down in the most recent version of the Declaration of Helsinki, with the exception that registration of such Phase 1 trials in a publicly accessible database is not mandatory.

This study will be conducted in compliance with the protocol. The protocol and any amendments and the subject informed consent will receive IRB/IEC approval/favorable opinion prior to initiation of the study.

All serious breaches must be reported to Biohaven (or designee) immediately. A Serious breach is a breach of the conditions and principles of GCP in connection with the study or protocol, which is likely to affect, to a significant degree, the safety or physical or mental integrity of the subjects of the study or the scientific value of the study.

Study personnel involved in conducting this study will be qualified by education, training, and experience to perform their respective task(s).

This study will not use the services of study personnel where sanctions have been invoked or where there has been scientific misconduct or fraud (e.g., loss of medical licensure, debarment).

The Principal investigator and the Sponsor's representative must sign the protocol and its amendments (if any) before initiating the study.

It is the Sponsor's responsibility to submit the protocol and its amendments (if any), and the Informed Consent Forms (ICFs) to regulatory authorities when necessary.

10.2 Data Monitoring Committee (DMC)

An independent DMC will be utilized for this study. The DMC will review the safety of all subjects enrolled in trials on a regular basis.

The DMC will review the protocol and will identify the data parameters and format of the information to be regularly reported. The DMC will meet in person or by conference call according to the schedule specified in the DMC charter. The DMC will typically receive reports with data by treatment group (e.g. blinded group A, group B etc.) or, if requested by the DMC, completely unblinded.

Based on the review of safety data, the DMC will make recommendations regarding the conduct of the study to the clinical team. These may include continuing the study as designed, amending safety monitoring procedures, modifying the protocol or the informed consent form, or recommending the termination of the study. In addition, the DMC statistician will conduct a futility analysis using the primary endpoint, after approximately half of the subjects have reached Day 15.

For purposes of the DMC, data analysis will be carried out by the unblinded safety biostatistics team independent and firewalled from the team directly involved with the study design and primary analyses, and a report will be prepared for the DMC.

For further details please refer to the DMC charter.

